8.5. Ocular Findings from Ophthalmic Exam (Part 2)

As outlined in study protocol (GSK Document Number.: [TMF-14344600](#)) Schedule of Activities (Table 7- Table 10 of Section 7), ophthalmic exams are scheduled at screening, during the study, end of treatment, and follow-up period. The ocular findings from ophthalmic exams will be analysed as described below.

1. From baseline to last follow-up, the following analysis will be performed:

a. Visual Acuity:

i. The best corrected visual acuity (BCVA) summary will be based on the Logarithm of the Minimum Angle of Resolution (logMAR score), where:

$$\text{logMAR score} = -\log_{10}(\text{Snellen Acuity Score})$$

The following categories of logMAR score changes from baseline are defined:

- No change/improved vision is defined as a change from baseline <0.12 ;
- A possible worsened vision is defined as a change from baseline ≥ 0.12 to <0.3 ;
- a definite worsened vision is defined as a change from baseline ≥ 0.3 logMAR score.

ii. A summary of characteristics of definite worsen vision as defined above by subject will be provided, including time to onset of first occurrence; outcome and duration of first occurrence; number of occurrences based on subjects with definite worsen vision; outcome post treatment exposure; time to resolution post-treatment exposure

iii. In addition, a summary of worst change from baseline (based on the eye with worst change) in BCVA score (logMAR score) will be provided for the following categories:

- Increase ≥ 0.12 to < 0.3
- Increase ≥ 0.3 to < 0.6
- Increase ≥ 0.6

iv. Number (%) of subjects with a decline in BCVA to 'light perception' (LP) or 'no light perception' (NLP) anytime post-baseline will also be provided.

b. Corneal Exam

i. Shift table from baseline to worst post-baseline by eye (R/L) and subject (worse eye, defined as the eye with the maximum worsening change from baseline) for corneal epithelium findings:

- Corneal epithelium (Normal to Abnormal), Corneal ulcer (No to Yes), Epithelial microcystic edema (No to Yes), Subepithelial haze (No to Yes), Corneal neovascularization (No to Yes), and Microcysts without edema (No to Yes)

- ii. For punctate keratopathy, summary Table of worst grade post-baseline and most frequent grade post-baseline across ocular exams by eye (R/L) and subject (worse eye)

- c. Lens
 - i. Shift Table from baseline to worst post-baseline by eye (R/L) and subject (worse eye, defined as the eye with the maximum worsening changes from baseline) for lens findings:
 - Lens: Clear (No to Yes), Pseudophakia (No to Yes); and Types of cataract (Nuclear Sclerosis, Cortical Cataract, Posterior Subcapsular Cataract).

The details of the planned displays are provided in [Appendix 11: List of Data Displays](#).

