3.0054	All Treated	See programming notes	Shift in Lens Exam Results from Baseline to Worst Post-Baseline	
Report for: Part 1, Part 2, and combined Part 1 and Part 2; Summarize by dose level (refer to Section 5.1 for ordering of dose level and omit 1.92 mg/kg if data is not available; Total; Refer to mid205678 (primary_01) Table 3.1000 and Table 3.1020 for guidance. Categories are "No" and "Yes"; Include the following lens exams: Lens Clear, Pseudophakia, Nuclear Sclerosis, Cortical Cataract, Posterior Subcapsular Cataract
 
Add the following footnote:
 
Note: Baseline percentage is based on N. Percentage for worst post-Baseline value is based on Baseline n.
	P-SAC [3], F-SAC [4]

Safety: Tables					
No.	Population	IDSL / Example Shell	Title	Programming Notes	Deliverable [Priority]
3.0055	All Treated	See programming notes	Summary of Best Corrected Visual Acuity Test (BCVA) Scores (logMAR score)	Report for: Part 1, Part 2, and combined Part 1 and Part 2; Summarize by: dose level (Refer to Section 5.1 for ordering of dose level and omit 1.92 mg/kg if data is not available) Total.; Refer to mid205678 (primary_01) Table 3.0730 for guidance.	P-SAC [3], F-SAC [4]
3.0056	Safety	See programming notes	Number (%) of Subjects with a Decline in Best Corrected Visual Acuity (BCVA) to LP or NLP due Anytime Post-Baseline	Report for: Part 1, Part 2, and combined Part 1 and Part 2; Summarize by: dose level (Refer to Section 5.1 for ordering of dose level and omit 1.92 mg/kg if data is not available) Total.; Refer to mid205678 (primary_01) Table 3.0740 for guidance.	P-SAC [3], F-SAC [4]

Safety: Tables					
No.	Population	IDSL / Example Shell	Title	Programming Notes	Deliverable [Priority]

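### Section 8.5 c states the direction for lens clarity as No to Yes, the reverse of loss of clarity, and Table 3.0054 does not set No as the worst value for Lens Clear

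*SAP*

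**What the plan says.** SAP Section 8.5, item c, plans a lens shift table that compares baseline with the worst post-baseline result. It is shown for right and left eye and per "subject (worse eye, defined as the eye with the maximum worsening changes from baseline) for lens findings". The directions given are "Lens: Clear (No to Yes), Pseudophakia (No to Yes", followed by three cataract types without a bracket.

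Item b of the same section, on the corneal exam, uses the same notation: "Corneal epithelium (Normal to Abnormal), Corneal ulcer (No to Yes), Epithelial microcystic edema (No to Yes", with further corneal findings in the same form.

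The display is Table 3.0054 in Section 16.11.7, titled "Shift in Lens Exam Results from Baseline to Worst Post-Baseline". Its programming note gives No and Yes as the categories, says "Include the following lens exams: Lens Clear, Pseudophakia, Nuclear Sclerosis, Cortical Cataract, Posterior Subcapsular Cataract", and points to two tables of another study for guidance. The table is due at both the primary and the final analysis.

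Section 8.5 also says that "ophthalmic exams are scheduled at screening, during the study, end of treatment, and follow-up period", so an eye can have several post-baseline results.

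**The concern.** A table of worst post-baseline values needs to know, for each item, which value is worse. So does a worse-eye rule based on the largest worsening. For ulcer, haze, pseudophakia or a cataract type, Yes is the abnormal or changed state, and No to Yes is the right direction. Lens clarity has the opposite polarity: Yes is the normal finding and losing it is Yes to No. The plan gives it the same label as the other items, which looks like a copied direction.

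At stake is how one row reports loss of lens clarity. Ocular findings on ophthalmic exam are a Part 2 secondary endpoint (Section 2.2). A programmer who takes the bracket as the worsening direction would sort Lens Clear the wrong way. The table could then show a new nuclear sclerosis for an eye whose Lens Clear row reads Yes to Yes.

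**Working it through.** The plan gives no figure to reproduce, so the check has two steps: read the notation side by side, then follow one eye through the rule.

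**1. Notation**

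| Item (Section 8.5) | Direction stated | Better state | Runs better to worse? |
|---|---|---|---|
| Corneal epithelium | Normal to Abnormal | Normal | yes |
| Corneal ulcer | No to Yes | No | yes |
| Epithelial microcystic edema | No to Yes | No | yes |
| Subepithelial haze, neovascularization, microcysts without edema | No to Yes | No | yes |
| Pseudophakia | No to Yes | No | yes |
| Lens clear | No to Yes | Yes | **no** |

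Lens clarity is the only bracketed item that runs the other way. Table 3.0054 lists No and Yes for all five lens items together and sets no separate worst value for Lens Clear. Nothing else in the SAP does so.

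**2. Consequence if the bracket is taken as the worsening direction**

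Take one eye that is clear at baseline (Yes) and has k post-baseline exams. The tabulated post-baseline value is the worst value if it occurs at any exam, and otherwise the other value.

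- *Worst = Yes (as written), permanent loss starting at exam j.* If j is 2 or later, the eye has at least one clear post-baseline exam, so the worst value found is Yes and the cell is Yes to Yes. Only j = 1 gives Yes to No. So k − 1 of k onset positions are shown as unchanged: 1 of 2, 2 of 3, 3 of 4, 5 of 6 and 7 of 8 for k = 2, 3, 4, 6 and 8.
- *Worst = Yes, any path with at least one not-clear exam.* There are 2^k − 1 such paths, and only the all-not-clear path gives Yes to No. The rest, 2^k − 2, are shown as unchanged: 6 of 7 (k = 3), 14 of 15 (k = 4) and 62 of 63 (k = 6).
- *Worst = No.* Each of these paths is shown as Yes to No, for every k tested (1, 2, 3, 4, 6, 8).
- *Not clear at baseline, with post-baseline results No, Yes, No.* Worst = Yes gives No to Yes, which the stated direction counts as worsening. Worst = No gives No to No.

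These are counts of possible paths, not probabilities. The SAP gives no rate or time course for lens change.

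**3. Worse eye**

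Suppose the fellow eye stays clear throughout (Yes to Yes).

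- If the affected eye has at least one clear post-baseline exam, it is also Yes to Yes under worst = Yes. The two eyes tie, and the subject is shown as unchanged.
- If the affected eye is not clear at any post-baseline exam, it is Yes to No, which the stated direction treats as moving away from the worse state. The unchanged fellow eye then has the larger worsening and is chosen. Only here is the choice itself reversed.

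**The case against.** The strongest reply is that the bracket need not be a derivation rule. The SAP nowhere says outright that Yes is the worst value for Lens Clear, and Table 3.0054 names two categories without ordering them. A programmer could take worst in its ordinary sense, treat No as worst, and produce a correct row. The table also refers to displays of another study that are not in this document and may rank lens clarity properly.

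Part of this stands. What the finished table would show is conditional on the bracket being followed, and the reference displays cannot be assumed either to correct or to repeat the direction. But reading the bracket as a plain list of categories goes against the better-to-worse pattern of the corneal items. On that reading the worst value for Lens Clear would be left unstated, and the same line would still be needed.

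A reader might also infer more than the text supports:

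- *That every lens losing clarity is shown as unchanged.* An eye not clear at every post-baseline exam still appears as Yes to No.
- *That new opacities are hidden.* Nuclear sclerosis, cortical and posterior subcapsular cataract have their own rows in Table 3.0054, and Listing 1.0058 lists abnormal slit lamp lens results whatever the shift direction.
- *That nearly all new cases are affected.* This would need a clinical time course that the SAP does not give.
- *That the eye that stays clear always becomes the worse eye.* In the usual case the two eyes tie.

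**Conclusion.** The direction stated for lens clarity in Section 8.5 c is reversed, and Table 3.0054 does not repair it. This is an error in what is written, not merely a missing detail.

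The size is limited to the Lens Clear row of a descriptive, single-arm safety table. Taken as the worsening direction, that row shows an eye clear at baseline as Yes to Yes if it loses clarity after at least one clear post-baseline exam. An eye not clear at every post-baseline exam is shown as Yes to No but not counted as worsening, with the worse-eye choice affected in that case. The overall response rate is not touched. Nor is the Part 2 safety stopping rule, which counts treatment-related adverse events of Grade 4 or higher.

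The conclusion rests on two assumptions: that clear is the normal lens finding, and that the bracket means the same for the lens as for the cornea. The conclusion about the tabulated cells further assumes that the programmer follows the bracket.

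**What to change.** In Section 8.5 c, write the lens clarity item as Lens clear (Yes to No). In the programming note of Table 3.0054, state that No is the worst value for Lens Clear, both when deriving the worst post-baseline result and when choosing the worse eye. Leave pseudophakia and the three cataract types as they are.

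The cost is one line in Section 8.5, one added sentence in the table specification and one sort direction in the program. No new data are needed, no other display changes, and there is no evident drawback.

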8.6. Pregnancies

While pregnancy itself is not considered to be an AE or SAE, any pregnancy complication or elective termination of a pregnancy for medical reasons will be recorded as an AE or SAE as described in the protocol. If subjects and subjects' partner become pregnant while on the study, the information will be included in the narratives and no separate Table or listing will be produced.

8.7. Clinical Laboratory Analyses

Laboratory evaluations including the analyses of Chemistry laboratory tests, Hematology laboratory tests, Urinalysis, and liver function tests will be based on GSK Core Data Standards. The details of the planned displays are in [Appendix 11: List of Data Displays](#).

Summary of change from baseline by scheduled visits using mean, median, standard deviation, minimum and maximum will be provided.

Summaries of worst case grade increase from baseline grade will be provided for all the lab tests that are gradable by CTCAE v4.03. These summaries will display the number and percentage of subjects with a maximum post-baseline grade increasing from their baseline grade. Any increase in grade from baseline will be summarized along with any increase to a maximum grade of 3 and any increase to a maximum grade of 4. The 'Any Grade Increase' column will include all cases where the worst-case grade is 1 or higher and the baseline grade is missing. Likewise the Increase to Grade X (where X=3 or 4) will include cases that are worst-case grade X and the baseline grade is missing. Missing baseline grade will be assumed as grade 0. For laboratory tests that are graded for both low and high values, summaries will be done separately and labelled by direction, e.g., sodium will be summarized as hyponatremia and hypernatremia.

For lab tests that are not gradable by CTCAE v4.03, summaries of worst case changes from baseline with respect to normal range will be generated. Decreases to low, changes to normal or no changes from baseline, and increases to high will be summarized for the worst case post-baseline. If a subject has a decrease to low and an increase to high during

the same time interval, then the subject is counted in both the “Decrease to Low” categories and the “Increase to High” categories.

For urinalysis laboratory tests results, occult blood, proteins, ketones, and glucose dipstick tests will be summarized. If the subject has a discrete value greater than 0 or a character value that is positive, then the subject is counted in the “Presence” category. Otherwise, the subject is counted in the “Absence” category.

The number of subjects with worst case urinalysis laboratory tests results will be summarized by the combination of specimen, method, test, and category. Subjects with a missing baseline value are to be assumed to have a negative baseline value.

- If the subject with “Presence” or “Absence” category at baseline does not change post-baseline, then the subject is counted in the “No Change” category.
- If the subject with “Presence” category at baseline changed to “Absence” category post-baseline, then the subject is counted in the “Decreased” category.
- If the subject with “Absence” category at baseline changed to “Presence” category post-baseline, then the subject is counted in the “Any Increase” category

Separate summary tables for hematology, chemistry, urinalysis, and hepatobiliary laboratory tests will be produced. Liver function laboratory tests will be included with hepatobiliary laboratory tests.

A supporting listing of laboratory data for subjects with abnormalities of potential clinical concern will be provided. A separate listing of laboratory data with character values will also be provided. For lab test values that can be graded, values of grade 1 or above are defined as values of potential clinical concern. For lab test values that can not be graded, values out of the normal range are defined as values of potential clinical concern.

Detailed derivation of baseline assessment is specified in Section [5.2](#).

Unless otherwise specified, the denominator in percentage calculation at each scheduled visit will be based on the number of subjects with non-missing value at each particular visit.

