3.0066	All Treated	OUR1B	Summary of Urinalysis Results (Discrete or Character Values) by Visit	Report for: Part 1, Part 2, and combined Part 1 and Part 2; Summarize by: dose level (Refer to Section 5.1 for ordering of dose level and omit 1.92 mg/kg if data is not available) Total. For protein, occult blood, ketones, and glucose dipstick tests, remove "increase" columns and "Worst-case post baseline" row for dose levels and add "presence" and "absence" columns.	P-SAC [3], F-SAC [4]
3.0067	All treated	UR1	Summary of Worst Case Urinalysis Results Post Baseline Relative to Baseline	Report for: Part 1, Part 2, and combined Part 1 and Part 2; Summarize by: dose level (Refer to Section 5.1 for ordering of dose level and omit 1.92 mg/kg if data is not available) Total. Include only 'n', 'No Change/Decreased' and 'Any Increase' categories	F-SAC [4]

Safety: Tables					
No.	Population	IDSL / Example Shell	Title	Programming Notes	Deliverable [Priority]
Laboratory: Hepatobiliary (Liver)					
3.0068	All Treated	LIVER1	Summary of Liver Monitoring/Stopping Event Reporting	Report for: Part 1, Part 2, and combined Part 1 and Part 2; Summarize by: dose level (Refer to Section 5.1 for ordering of dose level and omit 1.92 mg/kg if data is not available) Total. If less than 5 participants, produce listing instead.	P-SAC [3], F-SAC [4]
3.0069	All Treated	LIVER10	Summary of Hepatobiliary Laboratory Abnormalities	Report for: Part 1, Part 2, and combined Part 1 and Part 2; Summarize by: dose level (Refer to Section 5.1 for ordering of dose level and omit 1.92 mg/kg if data is not available) Total.	P-SAC [3], F-SAC [4]
3.0070	All Treated	LIVER11	Summary of Liver Restart/Re-Challenges	Report for: Part 1, Part 2, and combined Part 1 and Part 2; Summarize by: dose level (Refer to Section 5.1 for ordering of dose level and omit 1.92 mg/kg if data is not available) Total.	P-SAC [3], F-SAC [4]
ECG					
3.0071	All Treated	EG1	Summary of ECG Findings	Report for: Part 1, Part 2, and combined Part 1 and Part 2; Summarize by: dose level (Refer to Section 5.1 for ordering of dose level and omit 1.92 mg/kg if data is not available) Total.	P-SAC [3], F-SAC [4]

Safety: Tables					
No.	Population	IDSL / Example Shell	Title	Programming Notes	Deliverable [Priority]

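### In worst-case urinalysis Table 3.0067, a subject already positive at baseline can never count as Any Increase, so a rise to a higher positive level is reported under No Change/Decreased

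*SAP*

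**What the plan says.** Section 8.7 states that "occult blood, proteins, ketones, and glucose dipstick tests will be summarized". It then sets a two-way split. Presence is assigned under the condition "If the subject has a discrete value greater than 0 or a character value that is positive". For everything else: "Otherwise, the subject is counted in the “Absence” category". A missing baseline is handled by assumption: "Subjects with a missing baseline value are to be assumed to have a negative baseline value".

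The bullets that follow define worst-case change on these two categories alone. For a subject in either category, the first rule is that if the "category at baseline does not change post-baseline, then the subject is counted in the “No Change” category". A move from Presence to Absence is a decrease. For a subject starting in Absence, the increase rule is that if the "category at baseline changed to “Presence” category post-baseline, then the subject is counted in the “Any Increase” category".

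Table 3.0067 in Section 16.11.7 reports the result. It was added by amendment (Section 1.1), is produced for the final analysis only, and is titled as a worst-case summary relative to baseline. Its programming note reads: "Include only 'n', 'No Change/Decreased' and 'Any Increase' categories".

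**The concern.** The table's title and its column label promise something the rule cannot deliver. Worst case relative to baseline, with a column for any increase, suggests that a subject whose result went up will be found there. Once results are reduced to two categories the ordering among positive results is gone, and a rise within the positive range cannot be distinguished from a stable result. In the pooled column it cannot be distinguished from an improvement either.

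The same section keeps the ordering for CTCAE-gradable laboratory tests: any increase in grade over baseline is counted, with separate counts for increases to Grade 3 and to Grade 4. For urinalysis, the reference to a discrete value above 0 shows that the plan expects at least some results to carry a level.

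Changes in laboratory parameters are part of the Part 1 primary endpoint and a Part 2 secondary endpoint (Section 2.2). A reader of the final report who takes Any Increase at face value would understand the remaining subjects to be stable or better. Some of them may have worsened.

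**Working it through.** The SAP states no figure to reproduce here, so the check applies its rule to possible cases.

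**Step 1: apply the bullets of Section 8.7 to each kind of shift.** The levels are illustrative.

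| Baseline | Worst post-baseline | Category shift | Column in Table 3.0067 | By level |
|---|---|---|---|---|
| negative | 1+ | Absence to Presence | Any Increase | increase |
| missing | 1+ | assumed Absence to Presence | Any Increase | unknown |
| 1+ | 1+ | Presence to Presence | No Change/Decreased | no change |
| 1+ | 3+ | Presence to Presence | No Change/Decreased | increase |
| 1+ | negative | Presence to Absence | No Change/Decreased | decrease |

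The fourth row is the defect. It shares a column with the third and fifth rows, and no baseline-positive subject can reach Any Increase.

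**Step 2: count the kinds of upward shift that are hidden.** Let k be the number of positive levels. The SAP gives no dipstick scale, so k = 3 to 5 is an assumption.

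- All upward shifts: k(k+1)/2
- Counted as Any Increase (from Absence): k
- Hidden (between positive levels): k(k−1)/2
- Hidden share: (k−1)/(k+1)

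| k | All upward | Counted | Hidden | Hidden share |
|---|---|---|---|---|
| 3 | 6 | 3 | 3 | 2/4 = 50% |
| 4 | 10 | 4 | 6 | 3/5 = 60% |
| 5 | 15 | 5 | 10 | 4/6 = 67% |

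These are types of shift, not expected numbers of subjects. If levels are compared instead, all 6, 10 or 15 count as increases.

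**Step 3: look for another summary table that shows the rise.**

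- By-visit Table 3.0066 drops the increase columns and the worst-case row for these four tests, and uses presence and absence columns.
- Table 3.0065 summarizes urine concentration changes but is not identified as covering dipstick results.
- Figure 3.006 plots albumin/creatinine ratios above 2000 mg/g against serum creatinine, if more than 3 participants qualify. It does not address blood, ketones or glucose.
- Listings 1.0042 and 1.0043 hold individual values but give no counts.

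No planned summary table clearly counts rises between positive dipstick levels.

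**The case against.** The strongest reply is that this is a disclosed convention. Section 8.7 defines every category, and it uses the same logic for blood tests that CTCAE does not grade. There, a subject already high at baseline who goes higher has made no categorical change either. That parallel is fair, and it means the comparison with graded tests alone would be one-sided. It does not rescue the label, however. The column for non-gradable tests is called Increase to High, which describes exactly what it counts. Any Increase does not.

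A second reply is that the rule is not biased in one direction only. Because a missing baseline is taken as negative, any later positive in such a subject counts as an increase, possibly wrongly. This stands as a separate effect that could inflate the column. It does not recover any rise in a subject with a known positive baseline.

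A third reply is that little is lost in practice. About 40 subjects are planned (roughly 12 in Part 1 and 28 in Part 2), listings of that size can be read subject by subject, and no stopping or efficacy decision uses this table. This also stands, and it limits the importance of the point.

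Finally, the SAP gives no dipstick scale and does not say whether a trace result counts as positive. Any remedy tied to a named level, such as a column for increases to 3+ or higher, would presume something the document does not state.

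**Conclusion.** The point holds for Table 3.0067. Any Increase means newly positive, every rise from one positive level to a higher one is placed under No Change/Decreased, and worsening among baseline-positive subjects is missed in full.

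The number of subjects affected cannot be derived. A reader might infer an undercount of, say, 30% to 70%, by assuming that this share of subjects is positive at baseline and that worsening is independent of baseline status. Under those assumptions the reported rate is the true rate times (1 − baseline-positive share), so the percentage missed is simply the assumed share returned. The SAP supports neither assumption.

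A reader might also infer that renal toxicity is understated. The SAP does not support that. Chemistry tables (3.0059 to 3.0061), Table 3.0065, the albumin/creatinine plot, the adverse event tables by maximum grade and the two listings all remain. The defect is confined to one descriptive table. It is still worth correcting, because that table is the planned worst-case summary for urinalysis and its label is wrong for these subjects.

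**What to change.** In Section 8.7 and the programming note for Table 3.0067, where a result is recorded with a level (discrete or ordinal), compare the worst post-baseline level with the baseline level and count any step up as Any Increase. Keep Presence/Absence for by-visit Table 3.0066 and for results recorded only as positive or negative. Add a footnote to Table 3.0067 stating that, for those results, Any Increase means a change from Absence to Presence.

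The cost is a short SAP text change and minor reprogramming of one final-analysis table. It uses results already collected and adds nothing for patients or sites.
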